5. STUDY DESIGN

This study is a double-blind randomized phase II pilot trial testing the safety and efficacy of ultra-high dose diuretics compared to standard dose diuretics over 24 hours in acute decompensated heart failure. Subjects will be screened after admission to the hospital with decompensated heart failure following stabilization and will be consented and offered participation in the trial. Once consent has been obtained, baseline serum and urine measures will be obtained along with administration of randomized treatment assignment for a total of 2 intravenous doses bid. An ambulatory blood pressure monitor (ABPM) will be worn for a 48 hour period starting from randomization. Additional mechanistic measures including short renal lohexol clearance (2 hour), echocardiography, arterial tonometry, liver elastography, and nocturnal apnea-hypopnea index (Watch Pat) will be performed. Final endpoint assessment with repeat of all baseline measures including lohexol clearance, echocardiography, arterial tonometry, liver elastography, and nocturnal apnea-hypopnea index (Watch Pat) will be performed on Day 2 after the 24-hour intervention. A final phone call visit at 90 days will assess for adverse events and heart failure hospitalization over the post discharge period.

6. SELECTION AND ENROLLMENT OF PARTICIPANTS

6.1 Inclusion Criteria

1. Age \geq 18 years
2. Diagnosis of decompensated heart failure receiving intravenous diuretics
3. Ability to provide informed consent

6.2 Exclusion Criteria

1. Patients on home inotrope medications
2. Patients with Chronic Kidney disease stage V and end stage renal failure on dialysis
3. Patients lacking the capacity to consent for themselves
4. Known pregnancy or breastfeeding mothers
5. Complex congenital heart disease
6. Allergy to furosemide or bumetanide
7. Respiratory failure requiring non-invasive ventilation (CPAP/BiPAP) or invasive mechanical ventilatory support at the time of randomization
8. Hypotension with systolic blood pressure <80 mm Hg at the time of randomization
9. Acute coronary syndrome
10. Sustained Ventricular tachycardia requiring treatment in the last 48 hours
11. Patients weighing ≤ 40 kg

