Study Product, Dose, Route, Regimen	Patients will be randomized 1:1 to ultra-high dose (IV bumetanide 12.5 mg bid) vs standard dose (IV furosemide as twice the home dose of oral daily diuretic in furosemide equivalents administered bid) for 24 hours. Participants will undergo comprehensive physiological assessment at baseline and 24 hours with short Iohexol clearance for true glomerular filtration rate, apnea hypopnea index, electrocardiography, echocardiography, serum, and urine biomarkers. Patients will be monitored for side effects including muscle cramps, new onset atrial fibrillation (AF), sustained ventricular tachycardia (VT), symptomatic hypotension (MAP<60 or systolic blood pressure <80 mmHg), development of renal insufficiency and dialysis initiation.
Duration of Administration	Patients will be on therapy for 24 hours.

Statistical Methodology	The primary efficacy endpoint is urine output over 24 hours which will be compared by T test between the two groups. Primary safety endpoint will be incident decline in creatinine estimated glomerular filtration rate by 50% over 24 hours. Key secondary endpoints include weight change, NT-proBNP change, urine output, urine sodium excretion, creatinine, and cystatin C estimated GFR changes, apnea-hypopnea index, Iohexol glomerular filtration rate, serum and urine proteomic analyses, peripheral vein pressure and echocardiographic changes over 24 hours, estimated GFR at day 7 or discharge (whichever is sooner) will each be compared by T test between the two groups.
-------------------------	---

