3.2 Secondary Objectives

The secondary objectives of this study are

- a) To demonstrate safety of ultrahigh dose diuretics at 24 hours defined as development of renal insufficiency (creatinine estimated GFR decline of 50%), and hypotension (symptomatic MAP<60 or systolic blood pressure <80 mmHg).
- b) To determine mechanistic changes in cardiac function, sleep parameters and biomarker changes in response to ultrahigh dose diuretics compared to standard dose diuretics.
- c) To compare 24 hour change creatinine and cystatin C based changes in GFR with gold standard Iohexol clearance testing of GFR among the two diuretic strategies

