8.1.2 Enrollment, Baseline, and/or Randomization

After confirming eligibility, informed consent will be obtained. Following consent, patients will be randomized 1:1 to ultrahigh vs standard dose diuretic strategies.

Day 1 (0-24 hours)

After randomization, patients will undergo comprehensive baseline assessment including weight, echocardiogram, history, and physical examination. Initial randomized therapy will be administered at least 6 hours after last clinically administered dose of IV diuretic (or immediately if no IV diuretic has been administered in the last 6 hours). Participants will be urged to void their bladders and discard urine at baseline immediately prior to receiving study drug. All baseline testing will be performed when feasible once consent is obtained. Baseline testing will include blood sample testing for NT proBNP, creatinine, cystatin C and hematocrit. Urine collection for urine creatinine and sodium will be specifically collected timed 1-2 hours after the administration of study diuretic dose to allow estimation of urine sodium excretion. 32 ml of blood and 30 ml of urine will be stored for future analyses. Peripheral venous pressure will be recorded from existing IV lines through pressure transducer monitoring from study team.

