9. SAFETY ASSESSMENTS

9.1 Adverse Drug Reactions and safety aspects with bumetanide

Muscle aches and myalgias is a known side effect of bumetanide and will be assessed by a Likert questionnaire (scale 0-10). New onset atrial fibrillation, ventricular tachycardia will be assessed by review of telemetry monitoring. Blood pressure will be assessed before administration of each diuretic dose and if blood pressure is <80 mm Hg this will be reviewed by the PI and clinical team before administering subsequent diuretic dose.

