9.3 Specification of Safety Parameters

Renal function panel will be checked at least twice as is standard practice during intravenous diuresis and K and Mg replacement will be adjusted as per electrolyte panel checks with oral KCl and Mg repletion utilized as per clinical practice. Intravenous repletion will be used when oral therapy is not tolerated. In the presence of substantial hypokalemia (K<2.9 mEq/dl), the subsequent diuretic dose will be held until K repletion has been administered.

Blood pressure monitoring prior to each dose will ensure hemodynamic stability prior to administration of subsequent diuretic dose. If the systolic BP is <80 mmHg this will be reviewed by the PI and clinical team before administering subsequent diuretic dose.

During arterial stiffness measures, if aortic pulse pressure is greater than 50 mmHg (derived from brachial BP), we will forgo carotid tonometry and femoral blood pressure measures.

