10. INTERVENTION DISCONTINUATION

Discontinuation of the study intervention is recommended for any incapacitating and/or life-threatening side effect. Resuming the study medication will depend on an evaluation if the drug can be safely resumed. Patients may have to permanently discontinue study interventions and for this reason participation in this study if intolerable side effects persist.

At any point in time and for any reason, patients may withdraw voluntarily from participation in the study.

In the absence of any reason for premature termination as outlined above, participation will end for every patient after 6 months of trial participation.

Blood pressure will be assessed before administration of the second dose of assigned IV diuretic. In the event of symptomatic hypotension (symptomatic MAP<60 or systolic blood pressure <80 mmHg), the participant will be evaluated by the PI and study team and further dose of study medication will be suspended. The patient, PI and clinical team will be unblinded to allow the clinical team to make a determination of optimal subsequent plans of care and diuretic dosing.

Study stopping rules for safety

We will also implement Bayesian monitoring with utilization of an independent study monitor [name] who will have access to unblinded patient data as they accrue with continuous monitoring of safety. Among the high dose diuretic arm, assuming a probability of serious adverse events of 1/20 (5%) as prior information, we will monitor for 1) symptomatic hypotension (defined above) and 2) a decline in estimated GFR from 0-24 hours of >50%. Based on prior experience with this intervention, we formulated a Bayesian prior distribution for the adverse event rate p associated with this intervention, tantamount to observing 1 adverse event in 20 previous patients, or a 5% prior probability. Based on this prior, the Bayesian prior probability that the true adverse event rate exceeds 20% is only 6%. We have developed a stopping boundary, based on the Bayesian analysis of the accumulating data and the criterion that we would stop the trial if the posterior probability that the true AE rate exceeds 20% gets to 40% or more. This leads to the monitoring boundary at which point, we will pause the study and consider protocol modification and/or cessation of the study as appropriate. This decision will be discussed and made by the PIs from cardiology ([name], [name]) and nephrology ([name]) and statistician ([name])

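### Exclusion 8 and the pre-dose review test only for systolic pressure below 80 mmHg, so a patient who already meets section 10's suspend-and-unblind rule through symptomatic MAP below 60 can be enrolled and given dose 1

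*Combined protocol and SAP*

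**What the plan says.** **Entry.** Section 6.2, item 8 excludes "Hypotension with systolic blood pressure <80 mm Hg at the time of randomization". It has no MAP limb and no symptom limb.

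**Before each dose.** Section 9.1 has pressure taken before each diuretic dose, and "if blood pressure is <80 mm Hg this will be reviewed by the PI and clinical team". Section 9.3 makes clear that the pressure meant is systolic: "If the systolic BP is <80 mmHg this will be reviewed by the PI and clinical team". The only action tied to the threshold is that review. Section 9.4 confirms that pressure is recorded ahead of each study dose, so a reading exists before dose 1.

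**Safety definition.** The synopsis (section 1) lists "symptomatic hypotension (MAP<60 or systolic blood pressure <80 mmHg") among the monitored side effects, and section 3.2(a) defines the safety outcome as "hypotension (symptomatic MAP<60 or systolic blood pressure <80 mmHg"). The side-effect list in section 7.1 gives only the systolic limb.

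**On treatment.** Section 10 states: "Blood pressure will be assessed before administration of the second dose of assigned IV diuretic". It continues: "In the event of symptomatic hypotension (symptomatic MAP<60 or systolic blood pressure <80 mmHg), the participant will be evaluated" by the investigators, further study drug is suspended, and the patient, principal investigator and clinical team are unblinded. Symptomatic hypotension under this definition is also one of the two events followed by the Bayesian stopping rule in the high-dose arm.

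**Timing.** Under section 8.1.2 the baseline assessment follows randomization, and "Initial randomized therapy will be administered at least 6 hours after last clinically administered dose of IV diuretic", or at once if none was given in the preceding 6 hours.

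**The concern.** The protocol treats symptomatic MAP below 60 as reason enough to withhold study drug and break the blind, but it applies that limit only from dose 2 onward. Nothing in the text applies it at entry or before dose 1, and nothing explains why the limit should be looser before the first dose than before the second.

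Two things are at stake. The first is safety: a patient already past the trial's own withholding limit may receive a first dose, which in the ultra-high arm is 12.5 mg of intravenous bumetanide. The second is interpretation: a suspended dose, an unblinding and arguably a monitored safety event could come from the patient's state at entry and not from treatment. In an arm of 10, one such patient is visible.

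**Working it through.** The plan gives no figure on this point, so the check compares the rules and then works out which readings fall between them.

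**The rules side by side**

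| Step | Where | Systolic <80 | Symptomatic MAP <60 | Action |
|---|---|---|---|---|
| Entry | 6.2, item 8 | yes | no | exclude |
| Before each dose | 9.1, 9.3 | yes | no | review |
| Before dose 2 | 10 | yes | yes | suspend, unblind |
| Safety definition | 1, 3.2(a) | yes | yes | monitored or scored |

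**Formula (assumption).** The documents give no MAP formula. The usual cuff formula is MAP = (SBP + 2 × DBP)/3.

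**Worked reading, 85/45.** MAP = (85 + 90)/3 = 58.3. Systolic 85 is not below 80, so neither exclusion 8 nor the section 9 review is triggered. MAP 58.3 is below 60, so with symptoms the section 10 rule is met.

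**The two limbs catch different patients.** At 79/55, MAP = (79 + 110)/3 = 63.0: the systolic limb is met and the MAP limb is not.

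**Width of the gap.** MAP < 60 requires DBP < (180 − SBP)/2; the pulse pressure must then exceed SBP minus that bound.

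| SBP | DBP below | Pulse pressure above |
|---|---|---|
| 80 | 50 | 30 |
| 85 | 47.5 | 37.5 |
| 90 | 45 | 45 |
| 100 | 40 | 60 |

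The required pulse pressure rises quickly with systolic pressure, so the gap lies mainly at systolic 80 to 90, and symptoms must be present as well.

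**Size if one such patient is enrolled (hypothetical).** With 10 per group (section 11.5.1, item 1.7.1) and two doses each, one patient losing dose 2 leaves 19/20 = 95% of planned doses in that arm and 1/10 = 10% of that arm unblinded.

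**Stopping rule.** If such a patient were in the high-dose arm and were counted, the section 10 table (columns read as patients treated) moves from 24% at 2 events in 4 to 42% at 3 in 4, and from 26% at 3 in 9 to 43% at 4 in 9. Both steps cross the 40% boundary. These are the printed values, taken as given.

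**Power.** The stated 80% at 1688 mL reproduces: a two-sample t-test with 9 evaluable per group (10 less 10% dropout) and SD 1200 gives 80.0%. No blood pressure rule enters that calculation.

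**The case against.** **Entry and on-treatment limits need not match.** This is true in general, and a more sensitive trigger on treatment is ordinary. The rationale in section 4.1 also expects blood pressure to improve with decongestion, and the retrospective data in section 10 show no difference in mean arterial pressure change with very high doses. But this explains neither admitting a patient who already meets the withholding rule nor giving dose 1 on a reading that would stop dose 2.

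**Other safeguards exist.** Patients are screened after stabilization (section 5). History and physical examination are part of the baseline assessment (8.1.2). Section 9.3 states a general aim of hemodynamic stability. Ambulatory monitoring runs from randomization, with readings every 30 minutes by day and hourly at night. Sections 7.3.3 and 11.1 keep out patients on, or expected to need, inotropes. These make the case less likely, and that part of the objection stands. None sets a MAP limit, and no action is tied to the ambulatory readings.

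**An unchanged baseline state may not be an event.** Section 9.5 defines an adverse event as absent at baseline or worsening from it. This makes it arguable whether the patient would count toward the stopping rule, or even trigger section 10. Section 10 states no baseline exemption, so the consequence is possible but not certain.

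**Stronger readings that a reader might infer.** One is that dose 2 is unprotected; section 10 covers it. Another is that hours pass between randomization and dose 1. The 6 hours run from the last clinical diuretic dose, and dosing may be immediate, so the documents give no such interval. A third is that only bumetanide patients are exposed; the gap applies to both arms.

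**Conclusion.** The mismatch is real and can be read directly from the text: the trial's own withholding limit is not applied at entry or before dose 1. It is a small safety and consistency gap, worth closing because closing it is easy.

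The documents do not show how many patients have systolic 80 or above, MAP below 60 and symptoms together, and the combination is probably rare. The 95% and 10% figures describe one assumed patient and do not predict that one will be enrolled. It would be wrong to infer that the primary comparison is compromised: no estimate, power or sample size figure changes. The conclusion rests on the standard cuff formula for MAP and on section 10's check applying to dose 2, as its wording says. Confidence is high for the mismatch and lower for its consequences.

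**What to change.** **Main change.** Reword exclusion 8 to cover hypotension at randomization in either form: systolic below 80 mmHg, or MAP below 60 mmHg with symptoms. Define symptomatic as symptoms that the investigator attributes to low blood pressure; the protocol does not define the term, and these patients already have symptoms of heart failure.

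**Before dose 1.** Apply the same definition to the pressure already taken. If it is met, delay dose 1 and review, then give it once a repeat reading clears. No unblinding is needed, because no study drug has been given. Keep the existing review for any systolic reading below 80, and leave section 10 as it is.

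**Editorial only.** Write systolic in section 9.1 and add the MAP limb to the section 7.1 list.

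**Cost.** A MAP value from an existing reading, a symptom question, and perhaps slightly fewer eligible patients. A randomized patient who never receives dose 1 would fall outside the primary analysis set, which requires some study diuretic (11.5.1, item 1.4.1). That loss should not depend on assignment, because the decision precedes study drug and is made by blinded staff (item 1.9.1). One such loss per arm, with no other dropout, stays within the 10% already allowed for. Section 4.5 expects 25 enrolled to accrue 20 but gives no reason for the surplus, so it should not be counted on to cover this.

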6.3 Study Enrollment Procedures

Eligible patients will be identified from screening of the hospitalized heart failure patients and approached in person for potential consent.

7. STUDY INTERVENTIONS

7.1 Interventions, Administration, and Duration

The ultrahigh dose diuretic arm will receive IV bumetanide 12.5 mg bid for 2 doses total within 24 hours. The standard dose diuretic arm will receive IV furosemide at usual doses (twice the home dose of oral daily diuretic in furosemide equivalents) administered as 2 doses total within 24 hours. Furosemide equivalents will be considered as follows (**40 mg of intravenous furosemide = 1 mg oral bumetanide or 40 mg of torsemide or 80 mg of oral furosemide** consistent with prior literature). There is variability in the reported literature on the conversion from torsemide to furosemide ranging from 1 mg: 1-2 mg conversion for torsemide to intravenous furosemide (JAMA 2023 Jan 17;329(3):214-223). We selected a 1:1 conversion from torsemide to IV furosemide for the standard of care arm to avoid excessively high furosemide doses for those on high doses of home oral torsemide such as 100 mg bid. The determination of diuretic dose for each of the two study drug administrations in the usual care group will be determined as twice the total home daily diuretic dose as IV furosemide split over 2 doses for bid administration. (See table for conversion of commonly used doses) If patients are diuretic naïve, they will be administered 40 mg IV bid if randomized to usual care. This will be the lowest administered diuretic dose in the standard of care arm. Therefore, if patients are on very low oral diuretic doses at home, they will be administered no lower a dose than 40 mg IV bid of furosemide for standard of care arm. The maximum allowable dose of IV furosemide in the standard of care arm will be 100 mg IV bid. Patients will be monitored for side effects including muscle cramps, new onset Atrial fibrillation (AF), sustained Ventricular tachycardia (VT), symptomatic hypotension (systolic BP<80), and dialysis initiation. Following the 2 study drug doses, patients will be subsequently treated by their physicians as per standard of care.

Home dose of diuretic	Study diuretic in standard of care arm
<80 mg of oral furosemide equivalent daily	40 mg furosemide IV bid
80 mg of oral furosemide equivalent daily	40 mg furosemide IV bid

(40 mg of oral furosemide bid or 20 mg torsemide oral bid or 80 mg of furosemide daily or 40 mg of torsemide daily or 1 mg of bumetanide daily)	
120 mg of oral furosemide equivalent daily (60 mg of oral furosemide bid or 30 mg torsemide oral bid or 120 mg of oral furosemide daily or 60 mg torsemide oral daily or 1.5 mg of bumetanide daily)	60 mg furosemide IV bid
160 mg of oral furosemide equivalent daily (80 mg of oral furosemide bid or 40 mg torsemide oral bid or 160 mg of furosemide daily or 80 mg of torsemide daily or 2 mg of bumetanide daily)	80 mg furosemide IV bid
200 mg of oral furosemide equivalent daily (100 mg of oral furosemide bid or 60 mg torsemide oral bid or 200 mg of furosemide daily or 120 mg of torsemide daily or 2.5 mg of bumetanide daily)	100 mg furosemide IV bid
>200 mg of oral furosemide equivalent daily	100 mg furosemide IV bid

Furosemide oral equivalent conversion

80 mg of oral furosemide = 40 mg of oral torsemide = 1 mg of oral bumetanide = 40 mg of IV furosemide

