In this pilot study we will therefore compare an ultra-high diuretic strategy with a conventional diuretic strategy in patients with decompensated heart failure with a primary efficacy end point of urine output at 24 hours. The primary safety endpoint will be a decline in serum creatinine estimated GFR by 50% of baseline value at 24 hours. This will be a double-blinded randomized pilot trial of ultra-high dose diuretics (IV bumetanide 12.5 mg bid for 24 hours vs IV furosemide at usual doses (twice the home dose of oral daily diuretic in furosemide equivalents administered bid). New initiation of adjunct diuretics (thiazide, SGLT2 inhibitors, acetazolamide, and spironolactone) will be discouraged during the 24-hour study period. Key secondary endpoints include weight change, NT-proBNP change, urine output, urine sodium excretion, creatinine, and cystatin C estimated GFR changes, apnea-hypopnea index, iohexol glomerular filtration rate, serum and urine proteomic analyses, peripheral vein pressure and echocardiographic changes over 24 hours, estimated GFR at day 7 or discharge (whichever is sooner) will each be compared by T test between the two groups.

4.2 Hypothesis:

Ultrahigh dose diuretic infusion will be associated with greater diuretic response and will not be associated with clinically significant decline in eGFR over 24 hours (defined as decline in creatinine estimated GFR of 50% from baseline at 24 hours).

4.3 Innovation:

1. Ultra-high dose diuretic strategies have not been compared to conventional diuretic strategies in a randomized trial
2. The use of a double-blind strategy will minimize bias in terms of diuretic adjustment and alternative therapies.
3. The measurement of serum and urine biomarkers of renal injury, peripheral vein pressure and echocardiography changes at baseline and at 24 hours will provide novel insight into the hemodynamic, renal, and cardiac response to decongestion.

4. The relationship between creatinine based GFR during non-steady state conditions such as active diuresis and extracellular volume reduction during diuresis, and true GFR measured by lohexol clearance testing has never been studied.
5. The effect of rapid diuresis on cardiac structure and function has not been well studied
6. The short-term effect of rapid volume removal on measures of sleep is unknown

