7.3 Concomitant Interventions

7.3.1 Allowed Interventions

All interventions necessary for the optimal medical therapy of the patients are allowed.

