7.3.3 Prohibited Interventions

Patients should not be on drugs that can significantly increase the risk side effects with bumetanide and furosemide, i.e., inotropic medications. New initiation of additional diuretic agents for synergistic diuresis (thiazide, acetazolamide, SGLT2 inhibitors and spironolactone) will be discouraged during the 24 hour study period to avoid electrolyte imbalance with potential randomization to very high dose diuretic arm. Following the 24 hour study period, addition of other diuretics and medications is as per the treating team per standard of care.

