
11. STATISTICAL CONSIDERATIONS

11.1 General Design Issues and possible approaches to address them

Muscle cramps is a possible side effect of high dose bumetanide infusions and may limit continuation of bumetanide therapy. In the event of severe muscle pain, the dose of subsequent blinded infusion can be decreased to half the infusion to minimize pain with analgesic use as needed. If side effect is severe requiring change in therapy despite electrolyte correction and decrease in diuretic dosing, patients will be unblinded with subsequent therapy provided as per clinical practice. Providers are variable in adjunct strategies with vasodilators, inotropes, and adjunct diuretics during management of acute decompensated heart failure. We will exclude patients with anticipated initiation or use of inotropes at baseline, and adjunct thiazide diuretics will be discouraged for the 24 hours during the study protocol. We will only recruit patients with

stable respiratory status without use of non-invasive or invasive mechanical ventilation to minimize need for rescue therapies.

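### Section 7.1 hands patients back to usual care after the second study dose, inside the 24-hour primary outcome window, while 7.3.3 does so at hour 24; neither expressly restricts non-study loop diuretic before then

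*Combined protocol and SAP*

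**What the plan says.** **Dosing and hand-over.** Section 7.1 gives the ultra-high arm "IV bumetanide 12.5 mg bid for 2 doses total within 24 hours"; the standard arm likewise receives two doses of IV furosemide within 24 hours. The same section then says: "Following the 2 study drug doses, patients will be subsequently treated by their physicians as per standard of care".

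**A second hand-over rule.** Section 7.3.3 uses a different trigger: "Following the 24 hour study period, addition of other diuretics and medications is as per the treating team per standard of care".

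**Restrictions inside the window.** Three places name the agents to be avoided:
- Section 7.3.3: "New initiation of additional diuretic agents for synergistic diuresis (thiazide, acetazolamide, SGLT2 inhibitors and spironolactone) will be discouraged during the 24 hour study period".
- Section 4.1: "New initiation of adjunct diuretics (thiazide, SGLT2 inhibitors, acetazolamide, and spironolactone) will be discouraged during the 24-hour study period".
- Section 11.1: "adjunct thiazide diuretics will be discouraged for the 24 hours during the study protocol".

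Section 7.3.1 is a broad permission: "All interventions necessary for the optimal medical therapy of the patients are allowed".

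**Safety pathways.** Under section 10, symptomatic hypotension suspends further study drug and leads to unblinding "to allow the clinical team to make a determination of optimal subsequent plans of care and diuretic dosing". Under section 11.1, a side effect that stays severe after electrolyte correction and dose reduction also leads to unblinding and clinician-directed therapy.

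**Outcome.** Section 11.5.1, items 1.3.1 and 1.4.1, defines and analyses urine output at 24 hours from the start of IV study diuretic, by intention to treat.

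**The concern.** The two sections give bedside staff different answers to one practical question: may the treating team order its own loop diuretic between the second study dose and hour 24? Read literally, 7.1 says yes and 7.3.3 suggests no.

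The trial tests a difference in loop diuretic dose. Open-label loop diuretic in that interval adds the same class of drug, and the resulting urine counts in the primary outcome. Clinicians can see urine output even when they are blind to assignment, so such doses would tend to go to patients with a poor response. If those patients were mostly in one arm, for example the standard arm, that arm's mean would rise and the contrast would shrink. The 24-hour eGFR endpoint and the other 24-hour changes share the window.

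Section 7.3.3 justifies its restriction by electrolyte risk in patients who may be in the very-high-dose arm. That reason applies equally to extra loop diuretic.

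**Working it through.** **1. When the 7.1 hand-over falls.** Both doses are given bid and within 24 hours, so dose 2 comes before hour 24. No clock time is stated. If bid means 12 hours apart (an assumption), the exposed interval is 24 − 12 = 12 hours. The potassium hold and blood pressure review in section 9.3 can delay dose 2 and so shorten it.

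**2. Whether any other text restricts non-study loop diuretic in that interval.**

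| Place | What it covers | Express limit on non-study loop diuretic, hours 0–24? |
|---|---|---|
| 4.1, 7.3.3 | New thiazide, SGLT2 inhibitor, acetazolamide, spironolactone; discouraged | No; loop agents not named |
| 11.1 | Adjunct thiazides; discouraged | No |
| 7.3.1 | Permits all necessary treatment | No |
| 7.1, 100 mg bid maximum | Control-arm study dose | No |
| 7.1, conversion table | Home dose converted to the standard-arm IV dose | No; suggests replacement, but holding the home drug is not stated for either arm |
| 8.1.2, 6-hour gap | Clinical IV diuretic before the first study dose | No; applies before hour 0 |
| 7.3.4, 12.3.4 | Recording of adjunct use and of deviations | No; at most implied |

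Continued home oral loop diuretic would also not be a new initiation.

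**3. The plan's own figure.** Inputs from section 11.5.1, item 1.7.1: SD 1200 mL, two-sided alpha 0.05, 10 per group, 10% dropout, hence 9 per group. For a two-sample t-test:
- standard error = 1200 × √(2/9) = 565.7 mL
- noncentrality at 1688 mL = 1688 / 565.7 = 2.98, with 9 + 9 − 2 = 16 degrees of freedom
- power from the noncentral t distribution = 80.0%

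The stated 1688 mL is reproduced. The relevant rows of the plan's table agree to within 1 point:

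| Difference (mL) | Stated power | Recomputed |
|---|---|---|
| 1500 | 70% | 70.2% |
| 1600 | 75% | 75.7% |
| 1700 | 80% | 80.5% |

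**4. Sensitivity scale.** From 1700 to 1600 mL costs 80.5 − 75.7 = 4.8 points; from 1600 to 1500 mL costs 75.7 − 70.2 = 5.5 points. A 100 mL shift in one arm's mean needs only 10 × 100 = 1000 mL of extra urine across 10 patients, or 9 × 100 = 900 mL across 9.

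As an illustration, with attenuation assumed and not taken from the documents:

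| Assumed loss of a true 1688 mL difference | Remaining difference (mL) | Power |
|---|---|---|
| 10% | 1519 | about 71% |
| 20% | 1350 | about 61% |
| 30% | 1182 | about 50% |

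These figures show what a lost contrast would cost. They do not show that one will occur.

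**The case against.** The strongest reply is that the documents largely settle the timing. The study summary, section 4.1, section 5 and item 1.1 of section 11.5.1 all describe a 24-hour regimen. A second bid dose covers its own dosing interval, so the next scheduled diuretic would fall at about hour 24. Section 7.3.3 is the specific rule on concomitant diuretics, and its deferral of other diuretics is not limited to non-loop agents. Section 12.3.4 lists deviations in diuretic administration separately from adjunct use, which suggests that off-protocol loop dosing would count as a deviation. Section 4.3 relies on blinding to limit differential diuretic adjustment.

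Most of this stands: hour 24 is the likely intention. It remains an inference, though, and 7.1 states a different trigger. Blinding to assignment does not stop a response to visibly low output.

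A reader might also infer that non-study loop use would go unrecorded. The documents do not support that. Adjunct use is collected (7.3.4), medications are assessed on Days 1 and 2 (Schedule of Events), and total in-hospital diuretic use is documented (8.1.3) and compared between arms (3.3 b). The gap is in the conduct rule, not in the data.

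A last objection is that a rescue exemption could let the same doses back in. This is fair if rescue is left open-ended, and the fix below narrows it.

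**Conclusion.** The inconsistency is real and worth correcting, as a cheap improvement. Section 7.1 as written releases patients inside the primary outcome window, 7.3.3 points to hour 24, and outside the two safety pathways no section expressly restricts non-study loop diuretic in between.

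The effect on the between-arm difference cannot be computed. It depends on how often such doses are given, how much urine they produce and how unequally they fall between arms, and the documents give none of these. The 12-hour interval is itself an assumption.

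A reader might infer that the primary analysis is biased or invalid, or that the stated power is wrong. Neither follows. The intention-to-treat analysis remains a valid comparison of two strategies, including whatever clinicians add, and the sample size calculation reproduces. What is at risk is how cleanly the result reflects the dose contrast that this pilot was set up to examine.

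**What to change.** 1. In section 7.1, replace the second-dose trigger: the return to physician-directed usual care begins after the 24-hour study period, defined as the end of the primary urine collection.
2. In section 7.3.3, add non-study loop diuretics, both IV and home oral, to the agents discouraged until hour 24. Keep rescue for clinical deterioration, and state that low urine output alone does not qualify. Leave the hypotension pathway (section 10) and the severe side-effect pathway (section 11.1) unchanged.
3. Keep the intention-to-treat analysis. Beside it, report by arm the number of patients given non-study loop diuretic before hour 24, and the doses. Total diuretic use is already to be compared; only the cut at hour 24 is new. This assumes that administration times can be read from the hospital records.

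The cost is two wording changes and one descriptive line from data already collected, with no added patients, procedures or urine collections. The downside is slightly less freedom for treating clinicians during part of one day.
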